In a phase 1 dose-finding clinical trial performed by the University of Chicago, patients with progressively metastatic solid tumors (after initial standard-of-care therapies) with at least two tumors amenable to SBRT were treated to a range of doses prior to initiation of immunotherapy. Pembrolizumab (200 mg IV every 3 weeks) was given within seven days after the final fraction of SBRT. The primary outcome was optimal RT dose; secondary outcomes included adverse events  $\geq$  grade 3, response rates, tumor control and survival. Seventy-three patients had 1-3 sites of metastatic disease treated with SBRT. No per-protocol reductions in radiotherapy dose were required. A total of six patients experienced grade 3 toxicity (pneumonitis, 3; colitis, 2; hepatotoxicity, 1) for an overall rate of dose-limiting treatment-related toxicity rate of 9.7%, providing evidence of safety and feasibility for stereotactic radiotherapy shortly followed by PDL1 blockade.

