**2.2 Secondary Objective(s)**

- 2.2.1 We plan to estimate overall survival in all patients and will compare overall survival of those randomized to radiation and consolidative immunotherapy against those receiving consolidative immunotherapy alone.
- 2.2.2 In patients who experience subsequent failures after initiating protocol directed therapy, we will assess whether these failures occurred at known or new sites of disease.
- 2.2.3 We plan to evaluate toxicity associated with the addition of consolidative radiation therapy to upfront chemoimmunotherapy followed by additional consolidative immunotherapy. This will include calculating rates of adverse events depending on treatment site. Potential toxicities reported would include pneumonitis, esophagitis, chest wall pain, dermatologic toxicity, renal dysfunction, gastrointestinal toxicity including nausea, vomiting, and diarrhea, hepatotoxicity, and abdominal pain. These toxicities would be assessed according to site of irradiation by the treating physician and graded as per CTCAE 5.

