## 7.0 Radiation Therapy Details

### 7.1 Timing of Radiation

If randomized to the consolidative radiation arm, then radiation therapy will begin within 21 days of randomization.

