  - c. The schedule above is standard of care for imaging followup. Should a patient be enrolled after starting maintenance immunotherapy and after their first 3 month followup scan, then they may be allowed to switch to 6 months interval imaging at 3yrs from the end of chemo-immunotherapy, rather than a full 3 yrs from the date of randomization in accordance with standard of care. At discretion of treating oncologist.
7. Definition of 1 mo. or 30 day followup
  - a. For patients randomized to RT, this time point is considered 30 days +/- 14 days from end of all radiation therapy treatments
  - b. For patients randomized to immunotherapy alone, this time point is considered 30 days +/- 14 days from the end of the 2nd cycle of on protocol maintenance immunotherapy
8. Two tubes of whole blood may be collected at time of registration or any time prior to initiating any protocol directed therapy and at the 1 month follow up +/- 2 weeks.
9. If patients progress and are not eligible for randomization, or if they progress at any point on the study, they are only followed w appendix L for survival after the point of progression

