## 13.0 Statistical Considerations

### 13.1 Power and Sample size

Based on previously published research and clinical experience, the predicted median progression-free survival (PFS) of patients treated with consolidation immunotherapy without SBRT is roughly 8 months measured from date of first chemo-immunotherapy treatment. We estimate that, considering this 8 month median survival in the “control” arm, with our projected sample size of 112 patients (randomized 2:1 to SBRT + immunotherapy vs immunotherapy alone), and considering a two-sided alpha of 0.05 and power of 0.80, that we will be able to detect a median survival of approximately 15 months from start of chemo-immunotherapy in the SBRT + immunotherapy arm. This calculation assumes a 54 month accrual period and a 5 year total follow-up period. This difference in median survivals (8 months vs 15 months) corresponds to a hazard ratio of 0.53. Randomization will be stratified by number of metastatic sites (1-3, 4-6, or 7-8.)

Given the design of this trial, not all enrolled patients will be eligible for subsequent randomization. We estimate that ~10% may have evidence of progression of disease on restaging with PET/MRI. Such patients would remain on study, but will only be followed for survival. Given this potential for a 10% decrease in randomizable patients, the final number needed to enroll is 125, in order to randomize 112.

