**13.3 Estimated Study Length**

We estimate approximately 4- 5 years for total enrollment. Data will be collected until patient death or for a period of 5 years whichever occurs first.

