**13.4 Interim Analysis Plan**

We have no planned formal interim analyses; however when we reach 50% of our planned accrual if 25% or greater have reached G3 or higher pneumonitis we will halt the study.

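### The pneumonitis halting rule in Section 13.4 does not say 25% of whom: 14 of 56 randomised, 16 of 62 or 63 enrolled, or 10 of about 37 in the radiation arm

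*Combined protocol and SAP*

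**What the plan says.** Section 13.4 plans no formal interim analysis but adds one safety look: "when we reach 50% of our planned accrual if 25% or greater have reached G3 or higher pneumonitis we will halt the study". That is the whole rule.

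Section 13.1 plans 112 patients, "randomized 2:1 to SBRT + immunotherapy vs immunotherapy alone", and 125 enrolled to reach that number. Accrual can therefore mean either figure. On timing, Section 13.1 says "This calculation assumes a 54 month accrual period and a 5 year total follow-up period", and Section 13.3 says "We estimate approximately 4- 5 years for total enrollment".

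The toxicity objective in Section 2.2.3 reads: "We plan to evaluate toxicity associated with the addition of consolidative radiation therapy to upfront chemoimmunotherapy". The one SBRT-plus-pembrolizumab study in the background (Section 1.7) had 73 patients with 1-3 treated sites: "A total of six patients experienced grade 3 toxicity (pneumonitis, 3; colitis, 2; hepatotoxicity, 1").

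The other safety provisions work event by event. Under Appendix R, unexpected grade 4 events, deaths and unplanned admissions over 24 hours go to the DSMC, which may suspend the trial. The pneumonitis table in Section 6.2 guides the care of single patients.

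**The concern.** A rule that stops the trial on a percentage needs a denominator. Here the choice decides the outcome. With 12 grade 3 or higher cases among 37 radiation-arm patients and none among 19 controls, the radiation-arm rate is 32% and the pooled rate is 12/56 = 21%. One reading halts the trial and the other lets it continue. Unless the reading is fixed beforehand, it would have to be chosen by people who have seen the counts.

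The rule also does not say when a case counts. The Study Calendar (Section 8.1) grades toxicity at 1 month, then every 3 months for 3 years and every 6 months for 2 years. The Appendix F form covers the last 30 days at the 1-month visit. The Appendix R reporting period is time on study treatment plus 30 days. These are three different windows.

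**Working it through.** **Inputs.** 112 randomised 2:1, 125 enrolled, about 10% lost before randomisation and 54 months of accrual (Section 13.1); 4-5 years of enrolment (Section 13.3); 25% at half accrual (Section 13.4). The rule states no patient count to reproduce. The enrolment figure does reproduce: 112/0.90 = 124.4, rounded up to 125.

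**Who is in the look.** Half of 112 is 56, expected as 56 × 2/3 ≈ 37 radiation and 19 control. Half of 125 is 62.5.

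**Trigger = smallest whole number at or above 0.25 × n.**
- All randomised: 0.25 × 56 = 14.
- All enrolled: 0.25 × 62 = 15.5 and 0.25 × 63 = 15.75, so 16. The patients never randomised are followed for survival only.
- Radiation arm: 0.25 × 37 = 9.25, so 10 (27.0%; 9 of 37 is 24.3%).

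**What the pooled trigger means in the radiation arm.** With no control case, 14/37 = 38%; with one, 13/37 = 35%; with two, 12/37 = 32%.

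**Where the verdicts conflict.** The radiation-arm reading halts and the pooled one does not when radiation cases are at least 10 and the total is under 14. That is 10-13 with no control case, 10-12 with one, 10-11 with two and 10 with three. The reverse also exists: 9 + 5 = 14 of 56 halts only when pooled.

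**How likely.** Let X be Binomial(37, pR) and Y be Binomial(19, pC), independent. Radiation-arm halt: P(X ≥ 10). Pooled halt: P(X + Y ≥ 14). Conflict: P(X ≥ 10 and X + Y < 14). The control rates of 0, 5% and 10% are assumptions; the documents give none. Every case is taken as known at the look.

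| True radiation-arm rate | Radiation-arm halt | Pooled halt, control 0 / 5% / 10% | Conflict, control 0 / 5% / 10% |
|---|---|---|---|
| 10% | 0.3% | 0.00 / 0.01 / 0.1% | 0.3 / 0.3 / 0.2% |
| 15% | 4.2% | 0.1 / 0.4 / 1.3% | 4.1 / 3.8 / 3.2% |
| 20% | 19.1% | 0.9 / 3.0 / 6.9% | 18.2 / 16.1 / 12.8% |
| 25% | 45.0% | 5.8 / 12.1 / 20.9% | 39.2 / 32.9 / 24.8% |
| 30% | 71.1% | 19.3 / 30.5 / 42.6% | 51.8 / 40.7 / 29.0% |
| 35% | 88.5% | 41.8 / 54.4 / 65.8% | 46.6 / 34.0 / 22.9% |

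The reverse conflict is at most 0.7% in every cell. At the cited study's 3/73 = 4.1%, both halting chances are below 0.01%.

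**Who has been treated by the look.** Accrual of 112/54 = 2.07 a month puts the look at 56/2.07 = month 27 (24 to 30 for 4 to 5 years). Radiation-arm accrual is 2.07 × 2/3 = 1.38 a month. Section 7.1 says "radiation therapy will begin within 21 days of randomization", so about 1.38 × 21/30.4 ≈ 1 patient may not have started. About 1.38 × 3 ≈ 4 were randomised in the last three months.

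**The case against.** The wording is not evenly balanced. A rule that opens with accrual most naturally counts accrued patients, and no section ties it to radiation. Pooling can be defended, since both arms receive immunotherapy and Section 9.2 lists pneumonitis among its complications. This stands: pooled is the likelier reading. It still leaves enrolled against randomised open, and it lets a radiation-arm rate above the sponsor's own 25% pass.

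A reader might infer that Section 2.2.3 makes the radiation arm the intended denominator. It does not. The effect of adding radiation is the difference between arms, and a radiation-arm rate alone cannot separate radiation from immunotherapy pneumonitis. The radiation-arm rate is recommended because it is not diluted by patients who receive no protocol radiation.

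A reader might also infer that severe pneumonitis would otherwise go unchecked. The documents do not support that. The non-mandatory guidance in Section 6.2 advises hospitalisation at grade 3-4. Appendix R sends unplanned stays over 24 hours to the DSMC, which records whether to suspend and may suspend the trial itself. That protection is real, though it has no rate threshold.

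Finally, the only documented rate is 4%, where no reading halts. That limits how likely a conflict is. A halting rule nevertheless exists for the unexpected case. This trial also allows up to eight sites and thoracic courses of 30-33 fractions, against 1-3 sites in the cited study.

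**Conclusion.** The concern holds in this form: the only rate-based halting rule has no stated denominator, arm or event window, and identical data can halt the trial or not. It should be fixed.

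The chance of conflict is 25-39% at a true radiation-arm rate of 25%, about 3-4% at 15%, 0.2-0.3% at 10% and nil at 4%. These figures rest on a 37/19 split, assumed control rates of 0-10% and complete reporting at the look. They do not show that a conflict is to be expected, only that the rule is unsettled in the range where it would be needed.

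**What to change.** Keep the sponsor's 25% and the half-accrual look. Before the look, amend Section 13.4 to state that:
- 50% of accrual means 56 randomised. Using 63 enrolled would give 63 × 112/125 ≈ 56 randomised, so timing barely changes.
- The rate is calculated by arm, and the rule applies to radiation-arm patients who have started protocol radiation.
- One named event window is used, reconciling Section 8.1, Appendix F and Appendix R.
- The control-arm rate and follow-up since radiation are shown beside it.

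Add a small table of halting chances for the number actually started. If the pooled rate is intended, state that beforehand with its own chances.

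The cost is one paragraph and a table, with no added patients or visits, and no added data if the window stays within what is collected. Events after progression would need new collection, because for patients who progress "they are only followed w appendix L for survival after the point of progression".

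The downside is more halts at true rates below 25%, since the trigger drops from 14 cases to 9-10. At a true 10% / 15% / 20% the chance is 0.3% / 4% / 19% for 10 of 37 and 0.8% / 8% / 28% for 9 of 36. Pooled, it is 0-0.1% / 0.1-1.3% / 1-7% (assumed control rate 0-10%). The radiation-arm denominator would still include patients treated only outside the chest.

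Separately, Section 9.4 omits the hospitalisation trigger that Appendix R includes; the two must be reconciled.

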**If randomized to consolidative radiation therapy then maintenance immunotherapy:**

Maintenance immunotherapy may NOT be delivered concurrently with consolidative radiation. Concurrently is defined as on the same day of any radiation treatment or on any day between the first and last treatment of radiation. Resumption of maintenance immunotherapy after completion of radiation therapy is at the discretion of the treating medical oncologist. They may resume maintenance immunotherapy as early as 24 hrs after the last radiation treatment, but resumption should be no later than 8 weeks from the last radiation treatment. If treatment related toxicities prohibit administration of maintenance immunotherapy, then restarting this therapy is at the discretion of the treating medical oncologist. In such cases, patients will remain on study until they experience progression or death. If they experience progression, patients will be followed for overall survival only per appendix L past the point of progression.

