### 7.2 Radiotherapy Dose and treatment methods

The total dose will be flexible based on the judgment of the treating radiation oncologist to respect normal tissue tolerances. Guidelines for suggested normal tissue constraints are listed below in section 7.6. Meeting these constraints are recommended, but not required for inclusion on the protocol. **Ultimately, dose selection is at the discretion of the treating radiation oncologist.** In general, for lung, liver, axial skeleton, and adrenal tumors, a dose of either 54 Gy in 3 fractions (fxs) or 5000 cGy in 5 fx using SBRT techniques will be appropriate if the GTV measures less than 5 cm. For tumors in these organs that are larger than 5 cm, or where normal tissue constraints are grossly exceeded, a dose of 3000-6000 cGy in 10 – 15 fractions may be more appropriate instead. In the case of an untreated primary with involved mediastinal lymph nodes, fractionated radiotherapy over the course of 30 – 33 treatments with or without concurrent chemotherapy may be necessary at the discretion of the treating physician and this is allowed.

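### The pneumonitis halting rule compares a to-date percentage with 25% at half accrual and sets no observation window, so it reads low and the limit acts as a higher one

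*Combined protocol and SAP*

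**What the plan says.** Section 13.4 plans no formal interim analysis but sets one safety condition: "when we reach 50% of our planned accrual if 25% or greater have reached G3 or higher pneumonitis we will halt the study". It names no denominator (enrolled, randomised or radiation arm), no minimum follow-up, no observation window and no pause in accrual while events mature. No other section supplies these.

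Other sections show how little of the relevant period a recent patient may have passed through:

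- Section 7.1: "radiation therapy will begin within 21 days of randomization".
- Section 7.2 allows, for an untreated primary with involved mediastinal nodes, "fractionated radiotherapy over the course of 30 – 33 treatments".
- Section 3.0, on immunotherapy after radiation: "resumption should be no later than 8 weeks from the last radiation treatment".

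On pace, Section 13.1 plans 112 randomised patients in a 2:1 ratio and states: "This calculation assumes a 54 month accrual period". Section 13.2 expects 1 to 4 patients per month. On numbers enrolled, Section 13.1 says "the final number needed to enroll is 125, in order to randomize 112".

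The plan does use an evaluability condition elsewhere. Section 14.2 scores local control only in patients with at least 4 months of radiographic follow-up, for a reason specific to imaging. Pneumonitis has no counterpart.

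**The concern.** A percentage of patients who have had an event so far equals the event rate only if everyone in the denominator has been observed long enough. At an accrual milestone that cannot be so. The newest patients may not have started radiation, or may have only just finished it. They add fully to the denominator and hardly at all to the numerator.

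The direction of the error is therefore known: the percentage is too low. This does not depend on which arm forms the denominator, or on the rule being applied only once. It matters because Section 13.4 holds the trial's only safety stop defined by a rate. A true rate at or above the stated 25% is less likely to trigger the halt than the wording suggests.

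**Working it through.** **No figure to reproduce.** The plan gives no operating characteristics for the rule, so the check starts from its inputs.

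**Inputs from the documents**
- 112 randomised over 54 months: 112/54 = 2.07 per month. Half accrual is 56 patients, reached at month 56/2.07 = 27.
- 2:1 allocation: 56 × 2/3 ≈ 37 in the radiation arm.
- Radiation starts 0 to 21 days after randomisation.
- Accrual range 1 to 4 per month: 56 patients are reached at T = 56 months (1 per month) or T = 14 months (4 per month).

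**Assumptions, not in the documents**
- Uniform accrual, and radiation start uniform over the 21 days (mean 10.5 days = 0.345 months).
- Time from start of radiation to G3+ pneumonitis, among those who will have it, is exponential with mean m of 2, 3, 4 or 6 months.

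**Step 1: share of eventual events visible at the look.** The visible share v is the average of 1 − exp(−t/m), where t is time since start of radiation (zero if not started). When T is long relative to m, this is close to

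v ≈ 1 − (m + 0.345)/T.

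For T = 27 and m = 3: 1 − 3.345/27 = 0.876. The table uses the full average, because the short form is too low at T = 14 with the longer means.

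**Step 2: the limit in effect.** The observed percentage is on average v times the true rate, so the true rate that shows as 25% is 0.25/v.

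| Mean onset | 1 per month: v, limit | 2.07 per month: v, limit | 4 per month: v, limit |
|---|---|---|---|
| 2 months | 0.96, 26.1% | 0.91, 27.4% | 0.83, 30.0% |
| 3 months | 0.94, 26.6% | 0.88, 28.5% | 0.76, 32.8% |
| 4 months | 0.92, 27.1% | 0.84, 29.8% | 0.70, 35.8% |
| 6 months | 0.89, 28.2% | 0.77, 32.6% | 0.59, 42.3% |

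**Step 3: chance of halting, radiation arm only.** With 37 patients, 9/37 = 24.3% does not halt and 10/37 = 27.0% does. The chance of halting is P(X ≥ 10) for X binomial with n = 37.
- True rate 30%: fully observed, 0.71. At the planned pace with m = 3, the visible rate is 0.30 × 0.876 = 26.3%, and the chance is 0.52.
- True rate 25%: fully observed, 0.45. The visible rate is 0.25 × 0.876 = 21.9%, and the chance is 0.28.

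**Step 4: a second onset model.** Take onset uniform over 3 to 6 months, after a lag of 1.9 to 2.9 months to the end of radiation. At 2.07 per month the limit then acts as 29–32%. The direction is the same and the size similar.

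**The case against.** **The documents do not say that every accrued patient counts as fully observed.** That is correct. Section 13.4 names no denominator, and a team could apply an unwritten follow-up requirement. What stands is that the rule, followed as written, has no such requirement.

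**Recent patients are not unobserved until their first scheduled follow-up visit.** A reader might add up the longest windows for radiation, immunotherapy restart and the one-month visit, and treat that span as blind. The documents do not support this. Section 6.0 has CTCAE measures at each immunotherapy cycle. Appendix R sends unplanned hospitalisation over 24 hours to the DSMC whatever the grade, with entry within 24 hours of first knowledge. Severe pneumonitis can be recorded before a scheduled visit. The calculation above does not use visit dates; the loss comes from short time at risk.

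**Individual SAE review already protects patients.** In part it does. Under Appendix R each reported SAE prompts a decision on suspending the protocol, and the DSMC may suspend the trial. But that process sets no rate limit. Pneumonitis is also listed in Section 9.2, so a grade 4 case without hospitalisation might be treated as expected.

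**The shift is small next to sampling error.** At the planned pace with mean onset 2 to 4 months it is about 2 to 5 points. One standard error at 25% with 37 patients is √(0.25 × 0.75/37) = 7.1 points. The comparison is fair, but sampling error falls on both sides of the true rate, whereas this shift always favours continuing.

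**Mixing the arms dilutes the rate more.** If controls are counted, 25% overall needs a radiation-arm rate of (0.25 − c/3)/(2/3): 37.5% for a control rate c of 0, or 35% for an assumed c of 5%. This is a separate matter that adds to the present one. It is also why the radiation-arm rate and onset delay should not be applied to all 56 patients: about 19 of them receive no protocol radiation.

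**Conclusion.** The concern holds for the rule as written. A to-date percentage at an accrual milestone, without an observation window, understates the G3+ pneumonitis rate for any of the possible denominators. At the planned 2.07 patients per month the 25% limit acts as about 27–33%. The effect is minor at 1 per month (26–28%) and large at 4 per month (30–42%).

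The direction follows from the wording of the rule. The size rests on an assumed exponential onset with mean 2 to 6 months and on uniform accrual. The documents do not support a claim that the rule cannot work, or that recent patients go unmonitored. The supported conclusion is that the rule is more permissive than the figure it states.

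**What to change.** Keep the look and the 25% limit. In Section 13.4, apply the limit to the estimated cumulative incidence of G3+ pneumonitis at a fixed time after the start of protocol therapy, and state:

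- the horizon and the denominator arm, both chosen by the sponsor;
- that death without pneumonitis is a competing event;
- how patients followed for survival only after progression (Sections 8.1 and 8.4.2) are handled, since their toxicity follow-up may end at that point.

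If a simple proportion is preferred, restrict both numerator and denominator to patients whose time since the start of protocol therapy has reached the horizon, whatever happened to them. Do not add later patients only because they have already had the event. That keeps recent cases and drops their event-free peers: under the model above with mean onset 2 to 6 months, a true 25% by the horizon reads as 28–29% for a 6-month horizon and 34–36% for 12 months, against 22–23% and 21–23% for the crude count.

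The cost is a few sentences of text and no extra patients or visits. The cumulative-incidence estimate has a somewhat wider interval. The simple proportion rests on fewer patients: for a 6-month horizon at the planned pace, (27 − 6 − 0.345)/27 × 56 ≈ 43 of 56, taking the same start delay in both arms.
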